2.2.2.3 Viral shedding

Time to cessation of viral shedding is defined as the time from treatment initiation to the time of first negative result with no subsequent positive results. Event is applicable only to patients infected at baseline. A value of 0.5 or less \log_{10} TCID₅₀/mL and a value of 0.26 or less \log_{10} vp/mL for Flu A strains and 0.3 or less \log_{10} vp/mL for Flu B strains will be interpreted as a negative result. Any subsequent missing values for either RT-PCR or culture will be assumed to be negative. Patients who did not have the right assay to determine viral shedding (Haemagglutination assay or NP-ELISA) will be excluded from this analysis.

- Time to cessation of viral shedding determined by Haemagglutination assay for H1N1 and Flu B strains or NP ELISA (NucleoProtein Enzyme-Linked Immunosorbent Assay) for H3N2 strains after viral culture and expressed in \log_{10} TCID₅₀/mL (50% Tissue Culture Infectious Dose).
- Time to cessation of viral shedding determined by RT-PCR and expressed in \log_{10} virus particles/mL (vp/mL).
- Incidence of patients with viral shedding by RT-PCR by visit.
- Incidence of patients with viral shedding by viral culture by visit.

- Incidence of persistent shedding, defined as $<1 \log_{10}$ vp/mL reduction at end of treatment, compared with baseline.

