4.4.2 Secondary Efficacy Endpoints

4.4.2.1 Time to Event Endpoints

Time to event endpoints include the following: TTR of all symptoms, TTR of individual symptoms, time to cessation of viral shedding and time to resolution of fever. These endpoints will be summarized using Kaplan-Meier tables and graphs. Viral shedding will be studied also per virus strain. The median TTR and associated 95% CIs will be estimated for each of the two treatment groups. The exact CIs of the median differences of Hodges-Lehmann (HL) estimators will be derived using the PROC NPAR1WAY in SAS. The protocol mentioned bootstrapping, however in SAS, bootstrapping calculates differences between medians, when the correct estimator in skewed distributions is the median of differences (or HL estimator). Asymptotic theory exists to obtain those CI (aka Moses CI).

Patients who have not experienced the event, e.g. resolution of all symptoms, by the last day of contact will be censored at this time. Patients who withdraw from the study without experiencing the event will be censored at the time of withdrawal (see [Appendix 7](#)).

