4.4.6.2 Removal of >48 hour symptom onset to dose restriction

Although the protocol originally specified this comparison would be restricted to those patients who received treatment within 48 hours (≤ 48 hours), such analysis will be conducted as a sensitivity analysis only. The rationale for the additional analyses is that there is no direct evidence that dosing more than 48 hours after the start of symptoms will not be effective. Whilst evidence from a large observational study suggests an increased benefit for patients if dosed within 48 hours, compared with patients dosed after 48 hours, there is still evidence of benefit if dosed more than 48 hours after symptom onset. In addition, IC patients can have prolonged viral shedding compared to immune-competent patients, suggesting that administration of drug after 96 hours after symptom onset may still provide benefit to these patients by limiting duration of their influenza.

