For the primary objective of evaluating the safety of oseltamivir conventional and double dose treatments, AEs, physical examinations, tissue rejection and/or graft versus host disease in transplant patients, laboratory tests, and vital signs will be summarized and compared with the known safety profile of the drug. For the summary of the development of resistance for each treatment arm, 95% confidence intervals will be provided with the estimated rates.

For the secondary objective of evaluating the efficacy of oseltamivir as measured by the time to resolution of influenza symptoms, the following two assessments will be made independently of each other and without regard to the outcomes in each case.

- Comparison to placebo control from pivotal registration trials

From the integrated efficacy database associated with the oseltamivir treatment approval, a population of placebo treated patients will be established that is comparable to patients in the current study whose first dose of study drug was within 48 hours of symptom onset. For this population, a median time to resolution of all clinical influenza symptoms will be determined along with its 95% confidence interval.

- Assessment of relative efficacy

The two dose groups will be compared to each other by estimating the difference in the median times to alleviation of symptoms and deriving an associated 95% confidence interval.

The following are the model-derived PK secondary endpoints for *oseltamivir and oseltamivir carboxylate*: steady-state AUC, C_{max} , and C_{trough} .

7. **APPENDIX 2: SCHEDULE OF ASSESSMENTS**

Table A2.1. Schedule of Assessments and Procedures

	Baseline	Treatment					Follow-up		
Study Day	1 (pre-dose)	1	2 or 3 ^{f,g}	6 ^{f,g}	8 ^{f,g}	11 ^{g,h,i}	15 ^g	40 ^{g,j}	
Informed Consent/Assent ^l	x								
Medical history	x								
Demographics	x								
Height and weight	x					x			
Pregnancy Test ^a	x					x		x	
Rapid diagnostic test for influenza virus shedding						x			
RIDTPCR/Culture for confirmation of influenza virus	x								
Safety Labs ^b	x					x			
Physical Examination	x					x		x	
Vital Signs (including pulse, respiratory rate, temperature, blood pressure)	x		x	x	x	x	x	x	
Nasal and throat swabs for viral shedding and viral load ^{c,d}	x		x	x	x	x	x	x	
PK sampling (blood) ^l						x ^m			
Review of patient diary data ^e			x	x	x	x	x	x	
Drug Administration		←—————→							
Collection of unused study drug and empty containers						x			
Previous Diseases	x								

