Previous/Concomitant medications	x	←—————→							
Adverse Events/Sec Illnesses and Treatments		←—————→							
Rejection, Graft versus host disease (GVHD)		←—————→							

- a. Urine pregnancy test for patients of child-bearing potential according to the judgment/discretion of the investigator.
- b. Hematology (CBC with differential) and chemistry (AST, ALT, total bilirubin, urea, Cr). Serum creatinine testing may be done at a local laboratory when clinically indicated to calculate creatinine clearance.
- c. Baseline swab samples will be assessed for the presence of resistance mutations.
- d. Two nasal and one throat swab for viral culture and RT-PCR.
- e. Influenza symptoms, temperature, and date/time of oseltamivir dose will be recorded by the patient in the patient diaries twice daily on Days 1 – 10, and once daily thereafter.
- f. A home visit may be made on Day 2 or 3 (for patients who are too ill to come into the clinic) and/or, Day 6, and/or Day 8; however, it is recommended that the PK blood draw be performed at the clinic.
- g. Day 2/3 visit window = + 1 day. Day 6 visit window = ± 1 day; Day 8 visit window = + 1 day. Day 11 visit window = ± 1 day. Day 15 and Day 40 visit occur approximately 5 and 30 days after the last dose respectively. Day 15 window = ± 1 day. Day 40 window ± 2 days.

- h. Only weight to be assessed. Height is not necessary at this visit. Study drug is taken on Day 11, only if the first dose was taken after 4 p.m. on Day 1.
- i. Patients who are rapid diagnostic positive can be treated per standard of care. They will be required to come for their follow-up visits on Day 15 and Day 40.
- j. Patients who discontinue treatment prematurely will have an end of treatment (Day 11) assessment at the time of treatment discontinuation or the following day. They will be required to attend their follow up visits approximately 5 and 30 days after the last dose (Day 15 and Day 40 assessments).
- k. Patients who discontinue during follow-up will have an end of follow-up (Day 40) assessment. This visit must occur within 30 days of the last dose.
- l. For patients who are unable to attend the clinic, swabs may be taken at home on those days where there is a home visit by site personnel.
- m. Plasma PK samples for assessment of oseltamivir and oseltamivir carboxylate will be collected from patients who give additional consent to participate in PK sampling using a sparse PK sampling approach.

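### Time to cessation of viral shedding is dated at the first negative swab and analysed as an exact time, so medians run late (badly so near or after Day 15) and the dose difference is unreliable when many patients still shed at Day 15

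*SAP*

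**What the plan says.** Section 2.2.2.3 has the endpoint "defined as the time from treatment initiation to the time of first negative result with no subsequent positive results", once for culture and once for RT-PCR. It adds: "Any subsequent missing values for either RT-PCR or culture will be assumed to be negative".

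The Appendix 2 schedule places the row "Nasal and throat swabs for viral shedding and viral load" pre-dose on Day 1 and on Days 2 or 3, 6, 8, 11, 15 and 40. Its footnote g says "Day 15 and Day 40 visit occur approximately 5 and 30 days after the last dose respectively", with Day 15 ± 1 day and "Day 40 window ± 2 days".

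Section 4.4.2.1 lists the time-to-event endpoints as "TTR of all symptoms, TTR of individual symptoms, time to cessation of viral shedding and time to resolution of fever". They are summarised by Kaplan-Meier, and for the arm difference "The exact CIs of the median differences of Hodges-Lehmann (HL) estimators will be derived using the PROC NPAR1WAY in SAS". Only right censoring is provided for, at last contact or withdrawal. No method for interval-censored times is named, and no limitation is stated.

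Section 4.4.6.2 notes that "IC patients can have prolonged viral shedding compared to immune-competent patients".

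**The concern.** A swab schedule does not observe the moment of clearance. It shows only that clearance fell after the last positive swab and no later than the first negative one. The plan takes the right-hand end of that interval as the event time. If negative results are true negatives, the recorded time can never be earlier than the true time. A patient who clears just after the Day 15 swab is recorded at about Day 40.

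Appendix 5 makes this endpoint's Kaplan-Meier analysis the main dose-response analysis for shedding and also uses it in a benchmarking plot against historical patients. Section 4.5 plots it against exposure. Section 4.4 reports treatment differences with confidence intervals only, so interval coverage is what a reader relies on. The SAP itself expects that shedding may be prolonged in these patients, and patients who shed past Day 15 are the ones caught by the long last gap.

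**Working it through.** **Inputs from the SAP.** Swab days as above. Nominal gaps, taking Day 2/3 as 2.5, are 1.5, 3.5, 2, 3, 4 and 25 days. With windows the last gap can run from Day 14 to Day 42, which is 28 days. There are 75 evaluable patients per arm (2.3).

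**The plan's own figure.** The SAP gives no expected median, effect or power for shedding. Its only power figure (66%, 2.3) is for symptom resolution: 75 per group, 34 h, SD 98 h and two-sided alpha 10% give 68.4% for two means, or 66.7% with the Wilcoxon efficiency 3/π applied to n. It is reproduced, but it does not bear on this endpoint.

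**Assumptions (not in the SAP).** Clearance time from first dose is exponential or Weibull with shape 2. The median pairs are assumed. Visits vary within their windows, no swab is missing and tests are error-free. A patient still positive at the last swab is entered at that swab's date. The Day 15 swab is about 14 days after first dose.

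**Step 1: medians.** Mean recorded median over 150 simulated trials, in days (conventional / double); late = recorded − true.

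| True | Exponential: recorded | late | Weibull: recorded | late |
|---|---|---|---|---|
| 8 / 6 | 9.7 / 7.4 | 1.7 / 1.4 | 9.4 / 7.5 | 1.4 / 1.5 |
| 12 / 9 | 18.0 / 11.1 | 6.0 / 2.1 | 15.2 / 10.6 | 3.2 / 1.6 |
| 14 / 10 | 24.5 / 12.3 | 10.5 / 2.3 | 25.8 / 12.2 | 11.8 / 2.2 |
| 18 / 12 | 36.4 / 18.0 | 18.4 / 6.0 | 37.6 / 14.8 | 19.6 / 2.8 |
| 20 / 15 | 36.9 / 28.0 | 16.9 / 13.0 | 38.0 / 32.7 | 18.0 / 17.7 |

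The delay is 1.4 to 2.3 days for true medians of 6 to 10 days, about 3 to 6 days at 12, and 10.5 to 19.6 days from 14 upwards.

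When the arms straddle Day 15, the difference of Kaplan-Meier medians is inflated. At 18 vs 12 (true difference 6) it averages 18.4 (exponential) or 22.8 (Weibull).

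**Step 2: Hodges-Lehmann difference and its 95% interval.** 200 trials per row; exact times → first-negative times.

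| True medians | Distribution | Mean HL (days) | CI width | Coverage on first-negative times |
|---|---|---|---|---|
| 12 vs 9 | Weibull | 3.08 → 2.95 | 3.9 → 6.0 | 95% |
| 12 vs 9 | exponential | 2.36 → 1.18 | 6.7 → 4.5 | 77% |
| 14 vs 10 | Weibull | 3.63 → 3.47 | 4.4 → 9.0 | 94% |
| 14 vs 10 | exponential | 3.48 → 1.28 | 7.6 → 5.0 | 53% |
| 18 vs 12 | Weibull | 5.84 → 3.12 | 5.6 → 12.7 | 72% |
| 18 vs 12 | exponential | 4.55 → 1.30 | 9.6 → 4.9 | 33% |
| 20 vs 15 | Weibull | 4.65 → 1.06 | 6.4 → 3.7 | 13% |
| 20 vs 15 | exponential | 3.93 → 0.71 | 11.1 → 3.4 | 12% |

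At Weibull 8 vs 6 the HL estimate is unchanged (1.93 → 1.97). The Monte Carlo error of a coverage near 77% is √(0.77 × 0.23 / 200) ≈ 3 points.

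**Step 3: what drives it.** The share still shedding 14 days after first dose is 2^−(14/m) for an exponential with median m, and 2^−((14/m)²) for the Weibull.
- 12 vs 9: 2^−1.17 = 45% and 2^−1.56 = 34% (exponential); 2^−1.36 = 39% and 2^−2.42 = 19% (Weibull).
- 20 vs 15: 62% and 52% (exponential); 71% and 55% (Weibull).

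Once about half or more of both arms share the Day 40 date, most pairwise differences reflect visit spacing. Patients still positive at Day 40 do not explain this. For the Weibull at 20 vs 15 they are only 2^−((39/20)²) = 7% and 2^−((39/15)²) = 1%, yet coverage is 13%. For the exponential they are 26% and 17% and do add to the attenuation.

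**Step 4: does interval coding help?** An interval-censored Weibull model on the same swab data (exponential truth, so the model is correctly specified) gives 12.1 vs 9.1 for true 12 vs 9, with 95% coverage of the difference. For true 18 vs 12 it gives 18.5 vs 12.1, with 94% coverage.

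**The case against.** The strongest reply is that the damage depends on assumptions that the SAP does not supply. That stands. A reader might infer that first-negative dating always shrinks a dose benefit, perhaps by half, and always gives intervals that are too narrow. The SAP does not support this. With lognormal clearance and medians of 12 vs 9.5 days, a log-SD of 0.8 takes the shift from 2.07 to 1.13 with 82% coverage. A log-SD of 0.5 at the same medians gives 2.40 to 2.21, a wider interval (3.5 to 4.8 days) and coverage of 94-96%. The SAP says only that prolonged shedding can occur.

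Four further points:
- **Opposing rule.** Counting later missing results as negative moves dates earlier. It acts only where swabs are missing, and nothing ties its size to the delay, so it is not a correction.
- **Same schedule in both arms.** True, but this protects neither the difference nor its coverage, as Step 2 shows.
- **Secondary endpoint, no test.** This limits the consequence. The co-primary endpoints, safety and resistance, do not use this date.
- **By-visit proportions, viral-load change and AUC are also reported.** They do not use the event date and let a reader see the visit-level data. But 4.4.2.4 plans no between-arm difference for shedding, so they do not replace the comparison.

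First-negative dating is also a common and transparent convention, and Appendix 4 requests only the derived cessation time for historical patients. Both are reasons to keep the planned output.

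**Conclusion.** The concern holds as a weakness of a secondary analysis, not as an arithmetic error. The recorded medians are late by construction: by about 1 to 3 days when true medians are well before Day 15, and by roughly 10 to 20 days or more when an arm's median falls near or after it. The direction rests only on the swab schedule and true negative results. The sizes rest on the assumed distributions.

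For the Hodges-Lehmann difference and its interval, no general direction or size can be claimed. The effect is small for early or tightly spread clearance. With many patients still shedding at Day 15, attenuation is strong and coverage is poor (10-16% at 20 vs 15 days across the exponential, Weibull and both lognormal distributions tried). The interval may be narrower or wider than with exact times, and the difference of Kaplan-Meier medians can be inflated when the arms straddle Day 15. The SAP does not say which case to expect, so an analysis that respects the intervals should be pre-specified.

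**What to change.** In 2.2.2.3, in addition to the current definition, code cessation as the interval from the last positive swab (excluded) to the first negative swab with no later positive (included), right-censored at the last swab if still positive.

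In 4.4.2.1 and Appendix 5, for both culture and RT-PCR, add:
- a Turnbull curve per arm;
- an interval-censored accelerated failure time model giving the double/conventional time ratio with 95% CI (PROC LIFEREG accepts interval data), with the distribution named in advance.

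Keep the first-negative Kaplan-Meier and Hodges-Lehmann output beside these, for comparability with the historical studies. State that a median falling after Day 15 cannot be located more precisely than the Day 15 to Day 40 interval.

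The cost is SAP wording and modest programming, with no new data. The time ratio needs a distributional assumption: in simulation a lognormal model covered 93-96%, and 92.5% when the truth was Weibull. That is why it belongs alongside the planned analysis and not in its place.

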Study NV20234 is a double-blind, randomized, stratified multi-center trial of conventional and double dose oseltamivir in immuno-compromised (IC) patients. The conventional dose in adults (≥ 18 years of age) and adolescents (from ≥ 13 to < 18 years of age) is 75 mg twice daily (BID) for 10 days. In children (from 1 to < 13 years of age) the conventional doses are 30, 45, or 60 mg BID for 10 days based on body weight. Immunocompromised (IC) patients who develop an influenza-like illness with confirmed influenza from a positive rapid diagnostic test, PCR, or viral culture will be enrolled during the influenza season. Patients will be stratified by:

- Transplant type: hematopoietic stem cell transplant [HSCT] vs. solid organ transplant [SOT] (Protocol Version A and B) or transplant status yes vs. no (Protocol Version C onwards).
- The time between onset of influenza symptoms and treatment start (up to 48 hours) (≤ 24 hours vs. > 24 hours) (Protocol Version A and B) or the time between onset of influenza symptoms and treatment start (up to 96 hours) (≤ 48 hours vs. > 48 hours) (Protocol Version C onwards).
- Influenza vaccination status for current influenza season (yes vs. no).
- Age (≤ 12 years vs. > 12 years).

See section 4.4.5 for further description of subgroup analyses.

2.1 **PROTOCOL SYNOPSIS**

The Protocol Synopsis is in [Appendix 1](#). For additional details, see the Schedule of Assessments in [Appendix 2](#).

2.2 **OUTCOME MEASURES**

All endpoints (safety, resistance, efficacy and PK) are defined in the SAP (descriptions of the endpoints are in Section 2 and the statistical methods used to describe the endpoints are described in Section 4). There are two co-primary endpoints – safety/tolerability and resistance. It is worth noting that the primary endpoint of this study changed during the course of the study. ‘Time to Resolution of All Influenza Symptoms’ was the primary endpoint in versions A

and B of the protocol. However, this endpoint was relegated to a secondary endpoint to reflect the change in objectives introduced in Protocol Version C.

Baseline is defined for all endpoints as the pre-dose reading on Day 1.

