4.7 RESISTANCE

To support the co-primary objective of this study, the proportion and Clopper-Pearson 95% CIs of patients with post-baseline genotypic or phenotypic resistance among all patients will be summarized by treatment group. The mITTi population will be used whenever possible.

In addition, the following outputs will be included:

- Incidence of overall post-baseline resistance (i.e. developed after first visit) by age (≥ 18 years vs < 18 years old) and treatment group, split by flu type and subtype.
- Incidence of overall baseline resistance (i.e. observed at first visit) by age and treatment group, split by flu type and subtype in ITT population. N.B. Patients with baseline resistance are excluded from both ITTi and mITTi populations.
- Profiles (listings) of viral load in \log_{10} vp/mL for patients with phenotypic or genotypic resistance at baseline. Also listings of genotypic resistance and phenotypic outlier samples.
- Incidence of known OC resistance mutations in phenotypic outlier samples compared with phenotypically OC sensitive samples.
- Incidence (in %) of post-baseline resistance in patients with detectable viral shedding (in \log_{10} vp/mL) at EOT and during follow-up period, by treatment group, age (≥ 18 years vs < 18 years old) and flu type and subtype.
- Summary (median and CI) of the TTR by treatment group, split by post-baseline resistance status.
- Summary (median and CI) of the TTR by treatment group in patients with post-baseline resistance, split by flu type.
- Summary of viral load in \log_{10} vp/mL for patients with phenotypic or genotypic resistance at baseline.

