4.8 VIROLOGY

The main virology outputs are:

- Incidence of persistent shedding (%), defined as $< 1 \log_{10}$ viral load (vp/mL) reduction at end of treatment compared with baseline.
- Summary of IC_{50} at baseline and fold-change over time by treatment group split by flu type and subtype using descriptive statistics: mean, SD, median, IQR, range.

- Summary of viral load in \log_{10} vp/mL for patients with resistant phenotype or genotype at baseline (ITT).
- Summary of viral load change from baseline over time in \log_{10} TCID₅₀ (viral culture) (adults mITTi).
- Summary of viral load change from baseline over time in \log_{10} TCID₅₀ (viral culture) (paediatrics mITTi).
- Summary of viral load change from baseline over time in \log_{10} vp/mL (RT-PCR) (adults mITTi).
- Summary of viral load change from baseline over time in \log_{10} vp/mL (RT-PCR) (paediatrics mITTi).
- Incidence of patients with viral shedding in \log_{10} TCID₅₀/mL and in \log_{10} vp/mL by visit (adults and adolescents mITTi)
- Incidence of patients with viral shedding in \log_{10} TCID₅₀/mL and in \log_{10} vp/mL by visit (paediatrics mITTi).

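### Persistent shedding is defined by the log10 drop alone, so a patient who clears virus from a low baseline load is counted as a persistent shedder

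*SAP*

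**What the plan says.** The definition appears twice in the SAP in nearly the same words. Section 2.2.2.3 sets it as less than 1 log10 "vp/mL reduction at end of treatment, compared with baseline". Section 4.8, where it is the first output listed, has less than 1 log10 "viral load (vp/mL) reduction at end of treatment compared with baseline". Neither place adds a minimum baseline load, a ceiling on the end-of-treatment load, or a requirement that the end-of-treatment sample be positive.

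Section 2.2.2.3 does say when an RT-PCR result is negative. For Flu A it is "a value of 0.26 or less" on the log10 vp/mL scale. For Flu B the limit is 0.3, and a value up to that many log10 "vp/mL for Flu B strains will be interpreted as a negative result". These cut-offs stand in the paragraph on time to cessation of shedding. So does the restriction "Event is applicable only to patients infected at baseline". Neither is carried into the persistent-shedding bullet.

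Section 2.2 fixes the starting point: "Baseline is defined for all endpoints as the pre-dose reading on Day 1". Section 4.7 uses detectability at end of treatment, but only to choose the patients for a resistance output: "post-baseline resistance in patients with detectable viral shedding".

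**The concern.** A patient whose end-of-treatment sample is negative is, in ordinary language and by the SAP's own cut-offs, no longer shedding. The persistent-shedding rule looks only at the size of the fall. A patient who starts close to the cut-off has less than 1 log10 of room to fall, so even complete clearance cannot satisfy the rule.

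Three things follow:

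- The same report could show one patient as not shedding on Day 11 in the by-visit table and as a persistent shedder in another table.
- The error goes one way. It adds cleared patients to the persistent count and removes none, so it can only raise the reported rate.
- For these patients the result is settled on Day 1. Whether they clear or not, they are counted as persistent, so they carry no information about dose.

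The SAP also does not say what numerical value a negative sample takes when the reduction is computed. For some patients the classification therefore turns on an unstated programming choice.

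**Working it through.** The SAP gives no figure for this endpoint, so there is none to reproduce. The check applies the rule to the SAP's own cut-offs.

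**Inputs**

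- Rule (Sections 2.2.2.3 and 4.8): persistent if b − e < 1, where b is the baseline and e the end-of-treatment value, both in log10 vp/mL.
- Negative if e ≤ c, with c = 0.26 for Flu A and c = 0.30 for Flu B (Section 2.2.2.3).
- n, the value used for a negative sample: not stated. Two assumptions are run: n = c (kept at the cut-off) and n = 0.

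**Step 1: which cleared patients are called persistent.** For a cleared patient e = n, so the rule calls the patient persistent when b − n < 1, that is, when b < 1 + n. A patient positive at baseline has b > c. The affected baselines lie between c and 1 + n:

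| Type | Negative recorded as | Affected baseline (log10 vp/mL) | Width |
|---|---|---|---|
| Flu A | 0.26 | above 0.26, below 1.26 | 1.00 |
| Flu A | 0 | above 0.26, below 1.00 | 0.74 |
| Flu B | 0.30 | above 0.30, below 1.30 | 1.00 |
| Flu B | 0 | above 0.30, below 1.00 | 0.70 |

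A patient in this band who stays positive has e > c ≥ n, so the drop is again below 1. Both outcomes give the same label.

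**Step 2: Flu A examples**

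| Baseline → end of treatment | Drop | Persistent by the SAP rule | Positive at end of treatment | Persistent if positivity is also required |
|---|---|---|---|---|
| 1.1 → 0.26 | 0.84 | yes | no | no |
| 0.9 → 0 | 0.90 | yes | no | no |
| 1.2 → 0.26 | 0.94 | yes | no | no |
| 1.2 → 0 | 1.20 | no | no | no |
| 2.0 → 0.26 | 1.74 | no | no | no |
| 8.0 → 7.1 | 0.90 | yes | yes | yes |

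The third and fourth rows are the same clinical result, baseline 1.2 followed by a negative sample. The label changes only with the value given to the negative. Requiring positivity gives both rows the same answer and leaves the genuine case in the last row unchanged.

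**Step 3: a side case.** A patient at 0.26 on both occasions has a drop of 0 and is also persistent by the literal rule. Whether such a patient enters the analysis depends on whether the restriction to patients infected at baseline is meant to extend to this endpoint.

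**Step 4: size per patient.** Section 2.3 plans for 75 evaluable patients per arm. One misclassified patient moves an arm's rate by 1/75 = 1.3 percentage points, and by more where adults and younger patients are reported separately.

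**The case against.** The best reply is that the bullet sits in a section on shedding, below the negative cut-offs, and is named for shedding. A sensible programmer might require positivity without being told. That is possible, but the text does not say so in either place, and Section 4.8 repeats the bare rule with no cut-off nearby. The same point limits the criticism: the bullet does not redefine a negative result, so this is an omission. A reader might infer that the SAP contradicts its own definition of negative, but that goes too far. The inconsistency arises only when the rule is applied literally.

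A reader might also infer that the rule fails at the other end, because a patient falling from 7.0 to 5.5 log10 vp/mL is called not persistent while still shedding heavily. The document does not support treating that as an error. A log-drop measure of response is a legitimate choice when it stands beside a measure of positivity, and the SAP has one. The proportion shedding by RT-PCR at each visit is planned in Sections 2.2.2.3, 4.4.2.4 and 4.8 and has a main summary table in Appendix 5. Day 11 is a scheduled swab visit in Appendix 2. That patient is counted there as still shedding.

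A third tempting reading is that every cleared patient with a baseline below about 1.3 is misclassified, or that the reported rate is materially inflated. The first holds only if negatives are recorded at the cut-off; Section 2.2.2.3 allows lower values, and at 0 the limit is 1.00. The second needs a share of low-baseline patients that the SAP does not give.

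Finally, the consequence is limited. The endpoint is secondary and descriptive, no hypothesis is tested on it, and it has no row of its own in Appendix 5. All of that stands. It reduces the importance of the point but does not repair the definition.

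**Conclusion.** The point holds for patients who clear from a low baseline. As written in Sections 2.2.2.3 and 4.8, persistent shedding includes patients who are RT-PCR negative at end of treatment, if their baseline is below 1.26 (Flu A) or 1.30 (Flu B) log10 vp/mL with negatives kept at the cut-off, or below 1.00 with negatives set to 0. These limits rest on the literal rule, the SAP's own cut-offs and the two assumed values for a negative sample.

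How many patients this touches cannot be computed from the SAP. It may be few or none. Entry up to 96 hours after symptom onset, and infected populations defined by laboratory confirmation without a minimum load, allow low baselines but do not show that they are common. Neither co-primary objective, safety or resistance, rests on this output. It is a defect of definition worth correcting because the correction is simple and removes a possible conflict between two tables. It does not threaten the trial's main conclusions.

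**What to change.** In Sections 2.2.2.3 and 4.8, define persistent shedding by two conditions that must both hold: RT-PCR positive at end of treatment (above 0.26 log10 vp/mL for Flu A, above 0.3 for Flu B), and a reduction from baseline of less than 1 log10 vp/mL. Say that any patient negative at end of treatment is counted as not persistent. State the value assigned to a negative sample when viral load changes are computed. State also whether the endpoint is limited to patients infected at baseline.

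No further output is needed for patients who remain positive after a larger drop, because the by-visit shedding table already reports them. The cost is one or two sentences in the SAP and a small change to the derivation. The swab results needed are already collected.
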